**2 Study Rationale/Purpose**

Pasireotide (SOM230) is a novel multi-receptor-targeted analog that has high affinity for four of the five SST receptor subtypes (SSTR1, SSTR2, SSTR3 and SSTR5); it has a 40-fold higher affinity and 158-fold higher functional activity for the SSTR5 receptor than octreotide. Because of its broad receptor binding profile, pasireotide may be more potent in PLD than octreotide. In this randomized double blind placebo controlled trial we will compare SOM230 treatment to placebo for 12 months in patients with PLD. The primary endpoints will be assessed at 12 months and patients receiving placebo then crossed over to SOM230, permitting all participants to receive SOM230 for the subsequent two years. MRI will be used to assess liver volume – the primary endpoint, which will be assessed at baseline, end of years 1 and 3. This study will assess the efficacy and safety of SOM230 in reducing total liver volume and improving quality of life over 12 months (we will not be assessing efficacy at 24 months. The therapy way be effective in PLD but also may prove to be effective for many more patients with PKD which will be evaluated using eGFR and kidney volume using MRI.

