### 10.2 Statistical methods

Demographics and laboratory data will be plotted (e.g. box plots) and summarized by treatment group. Frequency distributions will be used to describe categorical values and basic summary statistics (mean, standard deviation, median, and inter-quartile range) used to describe continuous values. All tests will be two-sided with alpha level 0.05. For quantitative endpoints (e.g. change in kidney and liver volumes, renal function, and SF-36 scales) the two-group independent samples t-test will be used to test for an effect of treatment. Should the assumptions of normality and equality of variances be untenable, we will consider a data transformation or use of the Wilcoxon rank sum test. Both point estimates (mean) and 95% confidence intervals will be used to summarize treatment effects. For qualitative endpoints (e.g. presence or absence of response) we will compare treatment groups using the chi-square or Fisher's exact test as appropriate.

**Efficacy (Liver & kidney):** The primary analysis of treatment efficacy will follow intent-to-treat principles, attempting to include all randomized patients. For the primary endpoint (change in

liver volume) we will not be able to include anyone without a 12 month MRI (kidney volumes will be handled in the same way). For the “response” endpoints, those without a 12 month MRI will be included in the analysis as non-responders. Secondary analysis – Efficacy (QOL): We will have up to 5 longitudinal assessments of QOL for each patient. Repeated measures analysis of variance will be used to compare mean QOL profiles over time between treatment groups. Also, within patient rates of change or slopes in QOL measures will be estimated (using simple linear regression) and compared between groups using the two-sample t-test.

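### SF-36 is tested by three unranked methods at 0.05, one of which weights all patient slopes equally; one mixed model through month 12 should be the main QOL analysis

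*Combined protocol and SAP*

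**What the plan says.** Section 10.2 fixes the error level once for everything: "All tests will be two-sided with alpha level 0.05". The SF-36 scales then fall under three methods.

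- Together with the other quantitative endpoints: "For quantitative endpoints (e.g. change in kidney and liver volumes, renal function, and SF-36 scales) the two-group independent samples t-test will be used". If the assumptions look untenable, "we will consider a data transformation or use of the Wilcoxon rank sum test"; no rule says when.
- In the secondary QOL paragraph: "Repeated measures analysis of variance will be used to compare mean QOL profiles over time between treatment groups".
- In the same paragraph, as an addition: "within patient rates of change or slopes in QOL measures will be estimated (using simple linear regression"), with the resulting slopes "compared between groups using the two-sample t-test".

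No method is called the main one. No scale, time window, minimum number of visits or slope weighting is given for QOL. The section expects as many as five QOL assessments per patient, which allows for fewer. It states how patients without a 12-month scan are handled for liver volume, kidney volume and response, but has no such rule for QOL. Section 3.2 lists QOL at baseline, 12 and 36 months, and section 2 names "improving quality of life over 12 months" as part of the study's purpose.

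**The concern.** Two faults sit in the same paragraph.

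The first is freedom of choice. Three tests of the same scale, each at 0.05 and none ranked, give more than one chance of a nominally significant result. The reader of the report cannot tell which test was meant to carry the conclusion.

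The second is efficiency. A least-squares slope from two early visits is much noisier than one from a full set, yet the two-sample t-test on slopes gives both the same weight. A patient with one visit has no slope at all and drops out. A mixed model on the same data would use every assessment and weight it by the information it carries.

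At stake is the credibility of the QOL claim, a secondary endpoint that the study purpose names. The primary liver-volume comparison is not touched.

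**Working it through.** **1. The plan's own figure.** The only power statement that covers SF-36 is in section 10.2: a difference of at least one SD on any quantitative endpoint, with 15 placebo and 30 SOM230 patients, two-sided alpha 0.05 and 80% power. The standard error is SD x sqrt(1/15 + 1/30) = 0.316 SD. The detectable difference is (1.960 + 0.842) x 0.316 = 0.886 SD (0.906 SD with the t distribution). Power at 1 SD is 0.885 (0.871 with t). The statement reproduces, but for a single two-group t-test, not for the slope test with unequal visits.

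**2. Inputs for the slope test.**
- Dropout: 3 of 48 = 6.25% (section 10.2), and 15%, the discontinuation level that section 6.10 does not expect to exceed.
- Visit months: not fixed by the documents. The objectives list three time points, section 10.2 as many as five, and the column alignment of the QOL row in Table 8 is unreliable. Assumed: 0, 6, 12 months for year 1; 0, 6, 12, 24, 36 months for the whole study.
- Leavers: assumed to have months 0 and 6 only.
- QOL variance: not given. Let s2 be the error variance per visit and tau2 the between-patient variance of true yearly slopes.

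**3. Slope variance.** This is s2/Sxx, with Sxx the sum of squared deviations of the visit times.
- 0, 6: Sxx = 9 + 9 = 18 months squared
- 0, 6, 12: Sxx = 36 + 0 + 36 = 72
- 0, 6, 12, 24, 36 (mean 15.6): Sxx = 243.36 + 92.16 + 12.96 + 70.56 + 416.16 = 835.2

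Leaver against complete patient, the ratio k is 72/18 = 4 in year 1 and 835.2/18 = 46.4 over 36 months.

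**4. Loss from equal weights.** With a fraction f of leavers, the variance of the unweighted mean slope relative to the inverse-variance weighted mean is

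[(1 - f) + f k] x [(1 - f) + f/k].

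Year 1, k = 4:
- f = 0.0625: 1.1875 x 0.9531 = 1.13
- f = 0.15: 1.45 x 0.8875 = 1.29

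If true slopes vary (tau2 = s2), the year-1 slope variances become 2 + 1 = 3 and 8 + 1 = 9 in units of s2, so k = 3 and the losses are 1.08 and 1.17. With f = 0 the loss factor is 1.

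Over 36 months, k = 46.4:
- f = 0.0625: 3.8375 x 0.9388 = 3.60
- f = 0.15: 7.81 x 0.8532 = 6.66

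With tau2 = s2 these fall to 1.34 and 1.74. If leavers also have month 12, k = 835.2/72 = 11.6 and the loss at 6.25% with no slope variation is 1.6625 x 0.9429 = 1.57.

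**5. Chance of at least one false positive on one scale.** Three independent tests would give 1 - 0.95^3 = 14.3%, an upper reference. The tests share data, so null simulations were run on complete visits, taking the ANOVA as the group-by-visit test.
- Year 1 (0, 6, 12 months): 7.7% with 16 v 32 patients; 7.5% in a separate run with 15 v 30. Each method alone rejects about 5%.
- 36 months, five visits: 12.6% with complete data, 12.6% at 6.25% dropout and 11.5% at 15%.

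In year 1 with complete data the slope is (-6 y0 + 6 y12)/72 = (y12 - y0)/12, the 12-month change divided by 12. The change test and the slope test then give the same p-value, so the three methods are really two.

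**The case against.** The strongest reply has five parts.

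- **A reader might infer that the QOL result as a whole loses precision many times over.** The documents do not support that. The weighting fault belongs to the slope test alone; the change t-test and the ANOVA do not have it. The several-fold figures need slopes through month 36 and leavers at month 6. Section 2 moves placebo patients to SOM230 after month 12, so that window is not a randomized comparison. Section 6.9 also asks leavers for an early termination visit, which would lengthen some short series if SF-36 is collected there. This stands, and the conclusion rests on year 1.
- **A reader might infer that the method will be picked after the fact.** Nothing says so: all three analyses are prespecified. What stands is narrower: without a ranking, the plan does not exclude it.
- **A reader might infer that the ANOVA discards incomplete patients.** That is true of the classical form, but section 10.2 does not say which form it means, and the term is also used for likelihood-based models close to the remedy.
- **A mixed model is not better in every respect.** Section 6.9 lists lack of efficacy and disease progression among the withdrawal reasons. If patients with worse slopes leave early, precision weighting pulls the estimate toward completers, while the unweighted mean slope does not, provided each leaver still yields a slope. This stands as a real downside.
- **One model per scale leaves the multiplicity across scales.** Assuming eight scales with correlation 0.7 to 0.3, one method still gives 19-30% for at least one false positive. This stands, and is why a main scale must be named.

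None of this supplies the missing ranking or removes the equal weighting.

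**Conclusion.** The point holds, at moderate size. Section 10.2 applies three tests to each SF-36 scale at 0.05 with no main method, and one of them ignores differences in visit count that the plan itself allows for.

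In the randomized year the slope test's variance is about 1.13 times the efficient one at the planned dropout and about 1.3 times at 15%, less if true slopes differ between patients, and there is no loss with complete visits. The false-positive chance per scale is about 7.5-8% in year 1 and about 12% if 36-month data are used, against a nominal 5%.

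These figures rest on assumed visit months, on leavers contributing months 0 and 6 only, on the planned scan dropout applying equally to QOL, and on simulated normal data.

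**What to change.** In section 10.2, make one linear mixed model for each SF-36 scale the main QOL analysis: treatment, time and treatment by time, all available assessments through month 12, with the month-12 treatment contrast as the result. Name one main SF-36 scale or summary score and call the others exploratory. Label the change t-test, the ANOVA and the slope test as supportive, and report data after month 12 separately from the randomized comparison.

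The model assumes that data are missing at random, so keep the unweighted slope analysis as a sensitivity check and report the number of assessments per patient by arm.

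The cost is a few lines of wording and standard software, with no new data or patients. The price is that the method and the main scale are fixed before unblinding.

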**Secondary analysis–Kidney volume will be measured as part of the efficacy analysis:**

AEs (both patient and event counts) will be tabulated by organ system (neuro, GI, etc.), individually, by severity and, for each severity, by investigator-assessed relationship to study drug. Fisher’s exact test will be used to compare treatment groups regarding adverse events. Patients who received at least one dose of the randomized study drug will be included.

**Statistical power:** The primary endpoint is one year percentage change in liver volume. Prior data in untreated patients suggest a growth rate (SD) of 5(±3) % per year. We have planned a 2:1 randomization in order to allow as many patients as possible to receive SOM230. The goal is to detect up to a 7.3% percentage point decrease in the mean cyst growth using SOM230 LAR® Depot. With **15 placebo and 30 SOM230** patients, the study will have 80% power (alpha=.05, two-sided) to detect a 7 percentage point difference. To allow for dropouts (1 placebo and 2 SOM230 patients without endpoint data); the study will randomize 16 placebo and 32 SOM230 patients. For any quantitative endpoint the study is powered to detect a difference in treatment means of at least one standard deviation. Secondary endpoints include comparison of responder rates (based on liver and renal growth) and adverse event rates between the two groups. With 16 and 32 patients, a true placebo response (or adverse event rate) of 8 % (1 of 13) vs. 30, 40, or 50% for SOM230 can be detected with 45%, 70%, and 88% power, respectively.

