### 1.5.2.2 Pasireotide LAR in PLD patients

Preclinical studies in the PCK rat (a recessive model of polycystic kidney and liver disease) showed that the SST analog octreotide reduces cAMP levels in kidney and bile ducts and slows the progression of hepato-renal cystogenesis. We previously completed a double-blinded, randomized, placebo-controlled clinical trial (NCT00426153) using OctLAR over 1 year in forty-two patients with severe polycystic liver disease (PLD), due to autosomal dominant polycystic liver disease (ADPLD) or autosomal dominant polycystic kidney disease (ADPKD). By magnetic resonance imaging, the mean liver volume decreased from 5907 to 5557 ml (4.95 ± 7.00%) in the octreotide group (n = 28) compared with 5374 to 5361 ml (0.92 ± 7.00%) in the placebo group (n = 14). This difference (mean 4.95 *versus* 0.92%) was significant (P= 0.045). The self-reported SF-36 quality of life form demonstrated a significant improvement in perception of body pain and physical function in octreotide-treated patients. Moreover, three separate prospective clinical trials have now shown similar positive effects of SST analogs in ADPLD and ADPKD. A few other published reports relating to the use of SST analogs further substantiate these observations. All of these studies were limited by small numbers of enrolled patients with a

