short follow-up of 6-12 months. In order to evaluate whether SST analog therapy sustains retardation of liver and kidney growth beyond one year, our protocol design included a second year of open-label active therapy with OctLAR. We completed an open-label extension with OctLAR for 1 additional year, to assess safety & clinical benefits over 2 years (O→O) and examine drug effects in the placebo group who crossed over to OctLAR in year 2 (P→O). The primary endpoint was a change in total liver volume (TLV); secondary endpoints were changes in total kidney volume (TKV), glomerular filtration rate (GFR), quality of life (QOL), safety, vital signs, & lab parameters. Forty-one of 42 patients that received OctLAR (n=28) or placebo (n=14) in year 1 received OctLAR in year 2 (max dose 40 mg). Patients originally randomized to placebo (P→O) showed substantial reduction in TLV after treatment with OctLAR in year 2 (-7.66±9.69%; p=0.011). The initial reduction of TLV in the OctLAR group (O→O) was maintained for 2 years (-5.96±8.90%), although it did not change significantly during year 2 (-0.77±6.82%). OctLAR inhibited renal enlargement during year 1 (+0.42±7.61%), but not throughout year 2 in the O→O group (+6.49±7.08%); and in the P→O group in year 2 (-0.41±9.45%). Using pooled analyses of all individuals who received OctLAR for 12 months (n=40; in years 1 & 2), reduction in TLV was -6.08±7.58% (p=0.001) compared to net growth of 0.9±8.35% in the (P→O) group.

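### Section 10.2: the stated 80% power for a 7-point difference does not follow from the only SD given (3%); it implies an SD of about 7.7 that the paragraph does not state

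*Combined protocol and SAP*

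**What the plan says.** The power paragraph of Section 10.2 names one-year percent change in liver volume as the primary endpoint and gives these inputs:

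- Variability: "Prior data in untreated patients suggest a growth rate (SD) of 5(±3) % per year", citing references 4 and 37. No other numerical SD appears in Section 10.2.
- Target: "The goal is to detect up to a 7.3% percentage point decrease in the mean cyst growth".
- Power, for 15 placebo and 30 SOM230 patients: "the study will have 80% power (alpha=.05, two-sided) to detect a 7 percentage point difference".
- A general statement: "For any quantitative endpoint the study is powered to detect a difference in treatment means of at least one standard deviation". It carries no power figure and no SD in percentage points.

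Earlier in Section 10.2, for quantitative endpoints including change in liver volume, "the two-group independent samples t-test will be used to test for an effect of treatment".

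Section 1.5.2.2 reports much larger SDs for 12-month percent change in liver volume in the investigators' earlier octreotide trial:

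- Year 1: "4.95 ± 7.00%) in the octreotide group (n = 28) compared with 5374 to 5361 ml (0.92 ± 7.00%) in the placebo group".
- Pooled analysis: "reduction in TLV was -6.08±7.58% (p=0.001) compared to net growth of 0.9±8.35"%.
- Placebo patients after crossover: "showed substantial reduction in TLV after treatment with OctLAR in year 2 (-7.66±9.69%; p=0.011").
- Year-2 change in patients who stayed on octreotide: SD 6.82.

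The power paragraph refers to none of these.

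**The concern.** A reader who checks the power statement will use the one SD printed beside it, and will not get 80% or anything near it. On that SD the trial looks several times larger than it needs to be. On the SDs seen in the earlier trial it looks about right or somewhat short. The paragraph does not say which view the design took.

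Power depends strongly on the SD, so the missing assumption decides whether 80% is cautious or optimistic. That also bears on how a null first-year result would be read: Section 6.10 says the open-label extension ends if the year-1 analysis finds no efficacy, and does not expect a need to stop for lack of power.

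Two smaller points add to the uncertainty. The target is 7.3 points in one sentence and 7 in the next, and it is described once as cyst growth although the endpoint is liver volume.

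**Working it through.** **Inputs from Section 10.2.** n = 15 placebo and 30 SOM230; difference 7 (or 7.3) percentage points; two-sided alpha 0.05; two-sample t-test with 15 + 30 − 2 = 43 degrees of freedom; SD 3.

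**Formula.** The standard error is SD × √(1/15 + 1/30) = SD × √0.1 = 0.3162 × SD. The noncentrality is the difference divided by that standard error. Power is the probability that a noncentral t on 43 df falls beyond the critical value ±2.017.

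**The plan's figure with the plan's SD.** Standard error = 0.3162 × 3 = 0.949. Noncentrality = 7/0.949 = 7.38. Power = 0.9999999, against 0.80 stated. The following variants do not bring it near 80%:

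- one-sided test, 7.3 points, 16 and 32 patients, or a Wilcoxon test at its minimum relative efficiency of 0.864: all above 99.999%;
- SD enlarged to 3 × √2 = 4.24: 99.9%.

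**Working back from 80%.** With 15 and 30 patients, 80% power corresponds to a difference of 0.906 SD. Hence:

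- at SD 3, detectable difference = 0.906 × 3 = 2.72 points;
- for 7 points, implied SD = 7/0.906 = 7.72 (normal approximation 7.90);
- for 7.3 points, implied SD = 7.3/0.906 = 8.05 (normal approximation 8.24).

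**The one-SD sentence.** A difference of one SD with 15 and 30 patients has power 87.1%. If 7 points is read as one SD, the SD is 7 and power is 87%, not 80%. At SD 3, 7 points is 7/3 = 2.33 SD.

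**SD 3 in the placebo arm only.** By simulation (400,000 trials), the pooled-variance t-test reaches 80% power for 7 points when the SOM230 SD is about 9.9. With an unequal-variance t-test the SOM230 SD would have to be about 12.6. Neither value is in the plan.

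**Power at the SDs in Section 1.5.2.2** (exact t, same SD in both arms, 15 and 30 patients):

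| SD | Source in the earlier trial | Power, 7 points | Power, 7.3 points |
|---|---|---|---|
| 6.82 | year-2 change, continued octreotide | 89% | 91% |
| 7.00 | year 1, both arms | 87% | 90% |
| 7.58 | pooled 12 months on octreotide | 81% | 85% |
| 8.35 | placebo, as given in the pooled analysis | 74% | 77% |
| 9.69 | former placebo patients, year 2 on octreotide | 61% | 64% |

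The placebo SD of 7.00 and the 8.35 (given in Sections 1.3 and 1.5.2.2) appear to be two reports of the same year-1 placebo change, with means of 0.92 and 0.9. They should not be treated as independent ends of a range.

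**The case against.** The best defence is that the 3% was never the planning SD. It describes growth in untreated patients, and the paragraph does not say that it entered the power calculation. The one-SD sentence points to an SD of about 7. The target also resembles the pooled contrast in Section 1.5.2.2: 0.9 − (−6.08) = 6.98 points. With that sentence's SDs taken by arm (8.35 for placebo, 7.58 for SOM230), simulated power of the pooled t-test for 7 points is 78%. On this view a cross-reference is missing and the calculation may be sound.

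Much of this is fair, and it is why the sample size is not in question. It does not remove the mismatch. If 3% was not used, the paragraph states no planning SD and prints one that cannot be right for the 80%. The one-SD sentence gives no value and leads to 87%. The link to the pooled analysis is an inference, because the power paragraph does not cite it.

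Two narrower objections partly stand. First, 6.82 and 9.69 come from year-2 changes, not from a first-year randomised comparison, so 7.00 to 8.35 (power 87% to 74%) is the more comparable range. Second, the 9.9 for a SOM230-only SD depends on the pooled-variance test, which is conservative when the larger variance is in the larger arm (simulated type I error about 1.1%). An unequal-variance test would already have about 93% power there, which is why 12.6 is given beside it.

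**Conclusion.** The concern holds. The stated 80% does not follow from the only SD given with it: SD 3 yields power above 99.99% for 7 points, and 80% requires an SD of about 7.7, or about 8.05 for 7.3 points. The result assumes the planned two-sample t-test, a common SD in both arms, two-sided alpha 0.05, and 15 and 30 evaluable patients.

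This is a reporting error in the justification of the primary endpoint. It does not show that the trial is underpowered: at an SD of 7.58 the stated power is about right (81%). It should be corrected because power for 7 points ranges from 87% to 74% over the most comparable SDs in the protocol, and from 89% to 61% over all of them. Which SD was actually used cannot be determined from the documents.

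**What to change.** 1. The study statistician confirms the SD used for the calculation. A back-solved value such as 7.7 should not be inserted without that confirmation.
2. State that SD and its source in the power paragraph, and either replace the 5 (±3)% figure or explain how it relates to the planning SD.
3. Restate the power at that SD for 15 and 30 evaluable patients, using one target difference (7 or 7.3 points) worded as percent change in liver volume.
4. Add a line on sensitivity covering the 12-month SDs in Section 1.5.2.2 (6.82 to 9.69), noting that 7.00 to 8.35 are the most comparable.

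The cost is one or two sentences of protocol text once the SD is confirmed. No change to the sample size or the analysis is needed.

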## 6.10 Overall Study Stopping Rules

Stopping criteria for hyperglycemia and other side effects, e.g. related to changes in hematology, chemistry, or cardiac test values are **listed in section 6.8**. Pasireotide has already demonstrated acceptable tolerability and efficacy in several completed or ongoing clinical trials (**page 38 Investigator Brochure**) and the LAR formulation is being examined in a phase 3 study for treatment of Acromegaly NCT00600886; Novartis data on file, and for Cushing disease (sc formulation; CSOM230B2305] recently reported (Colao, Petersenn et al. 2012). In the latter study hyperglycemia-related adverse events occurred in 73% of patients necessitating 6% discontinuing study treatment Plasma glucose levels increased 10% from baseline compared with a 2% increase in placebo ( $P<0.02$ ) after commencing octreotide treatment and no patient developed diabetes in our prior somatostatin analog study using OctLAR.

Gastrointestinal problems are the most commonly reported AEs associated with the use of SOM230, (predominantly mild diarrhea grade 1 or 2, and nausea requiring no treatment or study discontinuation). In our prior somatostatin analog study in PKD, only 1/42 individuals discontinued that study after one year (due to steatorrhea) and none discontinued because they developed diabetes. Based on our prior experience and others' studies of tolerability and side effects associated with OctLAR (and also with lanreotide in PKD and PLD), we do not anticipate there will be patient discontinuation >15%, since both drugs have a similar tolerability profile (**Investigator brochure section 6.2**). Hence, we do not anticipate we will need to stop this study in this patient population due to lack of study power. If there is no efficacy found after the first year analysis is complete then we will terminate the open label extension. We will be monitoring each patient closely (**table 8**) for expected and unexpected drug side effects. If there are any

serious suspected adverse reactions (>1) that were unexpected these would be evaluated by the sponsor-investigator and the risk/benefit of study continuation would be analyzed. Novartis also reserves the right to stop the study (**section 13.1.3**).

- Colao, A., S. Petersenn, et al. (2012). "A 12-Month Phase 3 Study of Pasireotide in Cushing's Disease." New England Journal of Medicine **366**(10): 914-924.

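### The printed responder power shows no allowance for the plan's own rule that a missing 12-month MRI counts as non-response; on the more natural reading of the rates, the planned tests give less power than each printed figure

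*Combined protocol and SAP*

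**What the plan says.** Four statements bear on this point. All but the last are in section 10.2.

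- Missing scans, in the efficacy paragraph: for the response endpoints, "those without a 12 month MRI will be included in the analysis as non-responders". These patients stay in the denominator and count as failures.
- Expected missing data, in the statistical power paragraph: "To allow for dropouts (1 placebo and 2 SOM230 patients without endpoint data". That is 1/16 and 2/32, or 6.25% in each arm.
- Responder power, in the same paragraph and on all randomised patients (16 placebo, 32 SOM230), reads: "a true placebo response (or adverse event rate) of 8 % (1 of 13) vs. 30, 40, or 50% for SOM230 can be detected". The powers given for the three scenarios are 45%, 70% and 88%.
- Section 6.10 gives an upper figure for stopping treatment: "we do not anticipate there will be patient discontinuation >15" percent.

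Section 10.2 also fixes the error rate ("All tests will be two-sided with alpha level 0.05") and leaves the test open between two: "For qualitative endpoints (e.g. presence or absence of response) we will compare treatment groups using the chi-square or" Fisher's exact test.

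**The concern.** The responder sentence uses the full randomised numbers, 16 and 32. Those are the right denominators under the missing-scan rule. The rates, however, are called true rates and carry no visible reduction for patients who will be scored as failures whatever their liver volume did. If the rates describe scanned patients, the rule shrinks both rates and the gap between them, and the test has less power than one run on the listed rates.

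What is at stake is how a responder result that misses significance is read. The comparison is a listed secondary endpoint. Its stated power should be that of the analysis actually written, with the three expected missing scans in it.

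**Working it through.** **Inputs.** From section 10.2: n = 16 and 32; placebo rate p1 = 8% (1/13 = 7.7%); SOM230 rate p2 = 30%, 40% or 50%; two-sided alpha 0.05; Pearson chi-square or Fisher's exact test; 1/16 and 2/32 without endpoint data. From section 6.10: 15%, used only as a sensitivity value.

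**Method.** Exact power = sum over a = 0..16 and b = 0..32 of Bin(a; 16, p1) × Bin(b; 32, p2), counting only tables with p ≤ 0.05.

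**Step 1: the plan's own figures (45%, 70%, 88%).** With the stated rates and complete data, at 16/32:

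| Method | 30% | 40% | 50% |
|---|---|---|---|
| Pearson, exact enumeration | 39.7 | 69.8 | 89.8 |
| Fisher, exact enumeration | 34.6 | 62.2 | 83.5 |
| Normal formula, pooled variance | 38.4 | 66.5 | 88.2 |
| Arcsine formula | 48.1 | 73.9 | 90.3 |
| Likelihood-ratio chi-square | 47.7 | 73.3 | 90.4 |

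Neither planned test reproduces all three. Pearson comes within 2 points of 70 and 88 but not of 45; Fisher matches none. The plan does not name the method behind its figures.

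**Step 2: apply the missing-scan rule.** Analysed rate = rate among scanned patients × fraction scanned. At the plan's allowance the fraction is 15/16 = 30/32 = 0.9375:

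- placebo: 8% × 0.9375 = 7.5%
- SOM230: 30% × 0.9375 = 28.1%; 40% × 0.9375 = 37.5%; 50% × 0.9375 = 46.9%

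**Step 3: power on the analysed rates, still at 16/32.**

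| Test | 30% | 40% | 50% | Loss against the same test in step 1 (points) |
|---|---|---|---|---|
| Pearson | 36.2 | 64.9 | 86.5 | 3.5, 4.9, 3.3 |
| Fisher | 31.1 | 58.2 | 79.6 | 3.5, 4.0, 4.0 |

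A variant with a fixed count (15 and 30 scanned patients at the stated rates, plus 1 and 2 forced non-responders) gives 36.1, 65.1 and 86.8 for Pearson and 31.0, 58.3 and 79.8 for Fisher. Using 1/13 in place of 8% raises the step 3 values by about 1 point (Pearson 37.5, 66.2, 87.2; Fisher 32.2, 59.6, 80.6). All of these remain below 45, 70 and 88.

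**Step 4: sensitivity, 15% without a scan in both arms.** Multiplying by 0.85 gives 6.8% vs 25.5%, 34.0% and 42.5%. Pearson: 31.5, 57.5, 80.4. Fisher: 25.8, 51.9, 73.6. The loss within each test is about 8 to 12 points.

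**The case against.** The strongest reply is that a true response rate may mean the true rate of the endpoint as analysed, with missing scans already counted as failures. The move from 15/30 for the primary endpoint to 16/32 for response fits that reading, and then nothing needs to be multiplied down. Section 10.2 does not exclude it. It is the less natural reading because the same 8% also serves as an adverse event rate, to which the missing-scan rule does not apply. In addition, 1 of 13 sits close to the 14-patient placebo arm of the earlier octreotide trial in section 1.5.2.2, which suggests a rate among observed patients. The plan gives no source for the 1 of 13, so that link is an inference.

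A reader might go further and infer that the printed figures are plainly overstated because they leave out the missing scans. The documents do not support that. With the reduced rates, the arcsine formula gives 45.2%, 70.3% and 87.6%, and the likelihood-ratio test gives 45.2%, 69.7% and 87.6%. Both round to the printed 45, 70 and 88. This may be coincidence, and the plan names neither method, but the printed values could already contain the reduction under a method other than the planned tests.

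Two further points stand. The SOM230 rates are a grid of scenarios, and a shift of 3 to 5 points is small beside a printed range of 45% to 88%. And 15% is an upper bound on discontinuation, not an expected share of missing scans; section 6.10 reports 1 of 42 stopping in the earlier study.

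**Conclusion.** The point holds as a gap in a stated power. Section 10.2 shows no allowance for its own missing-scan rule. If the assumed rates are among scanned patients and missingness is unrelated to response, power at the plan's allowance is about 36%, 65% and 86% (Pearson) or 31%, 58% and 80% (Fisher).

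Two differences should be kept apart. The rule itself costs 3 to 5 points. The distance to the printed figures is larger (Pearson 8.8, 5.1 and 1.5 points; Fisher 13.9, 11.8 and 8.4) because neither planned test reproduces them even with complete data. Only the first difference is due to missing scans.

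The finding is minor. A reader might infer that the trial is undersized, but N was derived from the primary endpoint, percentage change in liver volume. Nor does everything categorical in the efficacy analysis rest on this one comparison: section 10.2 bases responder rates on liver and renal growth, and section 3.2 lists responders at both 12 and 36 months. The adverse-event use of the same sentence is unaffected by the rule.

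**What to change.** In the statistical power paragraph of section 10.2:

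1. Say whether the 8% and the 30%, 40% and 50% already count missing scans as non-response.
2. Name the planned test and the method used for the power figures.
3. If the rates are among scanned patients, replace 45/70/88% with power on the rates multiplied by the expected fraction scanned at the 3-patient allowance: 36.2/64.9/86.5% for Pearson or 31.1/58.2/79.6% for Fisher.
4. Show 15% missing as a sensitivity case only, labelled as an assumption.
5. Give adverse-event power in a separate sentence without the reduction.

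The cost is a few rewritten sentences and a less favourable stated power for a secondary endpoint. N and the analysis do not change.
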